2 ELIGIBILITY ASSESSMENT AND ENROLLMENT

2.1 ELIGIBILITY CRITERIA

2.1.1 Inclusion Criteria

- 2.1.1.1 Patients must have recurrent diffuse glioma (histologically confirmed by NIH Laboratory of Pathology) with *IDH1* or *IDH2* mutation (confirmed by DNA sequencing, FoundationOne is preferable for confirmation of mutation, but not necessary).
- 2.1.1.2 Patients must have tumor specific mutation burden (number of somatic mutations per exome) tested at NIH: Must have either result of tumor mutation burden from the most recent surgical tumor sample or must provide adequate genomic materials of the sample for tumor testing. The tumor tissue (e.g. block or 15 unstained slides) must be available for molecular and immune profiling. Fresh or frozen tumor sample will be used if available, but not mandatory.
- 2.1.1.3 Age ≥ 18 years. Because no dosing or adverse event data are currently available on the use of nivolumab in patients <18 years of age, children are excluded from this study, but will be eligible for future pediatric trials.
- 2.1.1.4 Patient must be able to tolerate an MRI study with intravenous gadolinium contrast.
- 2.1.1.5 Karnofsky $\geq 60\%$ ([Appendix A](#))
- 2.1.1.6 Patients must have adequate organ and marrow function as defined below:
 - Absolute neutrophil count $\geq 1,500/\text{mcL}$
 - Platelet Count $\geq 100,000/\text{mcL}$
 - Hemoglobin $> 9.0 \text{ g/dL}$ (may be transfused to achieve this level)
 - BUN $\leq 30 \text{ mg/dL}$ and

- Serum creatinine \leq 1.7 mg/dL
- Total bilirubin (except patients with Gilbert's Syndrome, who are eligible for the study but exempt from the total bilirubin eligibility criterion) \leq 2.0 mg/dL
- ALT **and** AST \leq 2.5x institutional upper limit of normal.

2.1.1.7 The effects of nivolumab on the developing human fetus are unknown. For this reason, women of child-bearing potential must agree to use adequate contraception (hormonal or barrier method of birth control; abstinence) prior to study entry and for the duration of study participation and up to 5 months (women). Should a woman become pregnant or suspect she is pregnant while she is participating in this study, she should inform her treating physician immediately.

2.1.1.8 The patient must be able to understand and be willing to sign a written informed consent document.

2.1.2 Exclusion Criteria

2.1.2.1 Patients who are receiving any other investigational agents.

2.1.2.2 Patients who have a history of receiving immune therapy.

2.1.2.3 History of allergic reactions attributed to compounds of similar chemical or biologic composition to nivolumab.

2.1.2.4 History of severe hypersensitivity reaction to any monoclonal antibody.

2.1.2.5 Prior invasive malignancy (except non-melanomatous skin cancer) unless disease free for a minimum of 3 years prior to initiation of study therapy.

2.1.2.6 Patients with active autoimmune disease or history of autoimmune disease that might recur, which may affect vital organ function or require immune suppressive treatment including systemic corticosteroids. These include but are not limited to patients with a history of immune related neurologic disease, multiple sclerosis, autoimmune (demyelinating) neuropathy, Guillain-Barre syndrome or CIDP, myasthenia gravis; systemic autoimmune disease such as SLE, connective tissue diseases, scleroderma, inflammatory bowel disease (IBD), Crohn's, ulcerative colitis, hepatitis ; and patients with a history of toxic epidermal necrolysis (TEN), Stevens-Johnson syndrome, or phospholipid syndrome. Such diseases should be excluded because of the risk of recurrence or exacerbation of disease.

Of note, patients with vitiligo, endocrine deficiencies including thyroiditis managed with replacement hormones including physiologic corticosteroids are eligible. Patients with rheumatoid arthritis and other arthropathies, Sjögren's syndrome and psoriasis controlled with topical medication and patients with positive serology, such as antinuclear antibodies (ANA), anti-thyroid antibodies should be evaluated for the presence of target organ involvement and potential need for systemic treatment but should otherwise be eligible.

2.1.2.7 The patient must not be currently on a corticosteroid dose greater than dexamethasone 1 mg per day or its equivalent.

2.1.2.8 Uncontrolled intercurrent illness including, but not limited to, ongoing or active infection, symptomatic congestive heart failure, unstable angina pectoris, cardiac

arrhythmia, or psychiatric illness/social situations (within timeframes identified in the bullets below) that would limit compliance with study requirements.

- 2.1.2.9 Known HIV-positive or acquired immune deficiency syndrome (AIDS) based upon current CDC definition; note, however, that HIV testing is not required for entry into this protocol. The need to exclude patients with AIDS is based on the lack of information regarding the safety of nivolumab in patients with active HIV infection.
- 2.1.2.10 Pregnant women are excluded from this study because nivolumab's potential for teratogenic or abortifacient effects is unknown. Because there is an unknown but potential risk for adverse events in nursing infants secondary to treatment of the mother with nivolumab, breastfeeding should be discontinued if the mother is treated with nivolumab.

2.1.3 Recruitment Strategies

Trial will be posted on www.clinicaltrials.gov, on other NIH websites and on NIH social media forums.

Patients may be enrolled from Natural History Study (NIH 16C0151), which includes all patients who have had their care for brain tumor at NOB. NOB patients are from entire United States.

Furthermore, the investigators plan to contact and network with existing Patient Advocacy Groups serving brain tumor organizations, including American Brain Tumor Association, National Brain Tumor Society.

2.2 SCREENING EVALUATION

2.2.1 Screening activities performed prior to obtaining informed consent

Minimal risk activities that may be performed before the subject has signed a consent include the following:

- Email, written, in person or telephone communications with prospective subjects
- Review of existing medical records to include H&P, laboratory studies, etc.
- Review of existing MRI, x-ray, or CT images
- Review of existing photographs or videos
- Review of existing pathology specimens/reports from a specimen obtained for diagnostic purposes

A waiver of consent for these activities has been requested in section **12.8.2**.

2.2.2 Screening activities performed after a consent for screening has been signed

The following activities will be performed only after the subject has signed the study screening consent. Assessments performed at outside facilities or on another NIH protocol within the timeframes below may also be used to determine eligibility once a patient has signed the consent.

The screening evaluation must be completed within 14 days prior to initiation of study therapy unless otherwise noted:

- Complete medical history and physical examination, including height, weight, vital signs, Karnofsky performance status (**Appendix A**: Performance Status Criteria and neurological exam (**Appendix B**). Height is optional and may be taken at any timepoint during the study, at the discretion of the investigator.

- Laboratory Evaluation
 - Hematological profile: CBC with differential and platelet count;
 - Biochemical profile: electrolytes, BUN, creatinine, AST, ALT, total bilirubin, calcium, phosphorus, albumin, magnesium, uric acid, amylase, lipase;
 - Serum pregnancy test for female participants of childbearing age (in the absence of prior hysterectomy) (24 hours prior to initiation of study therapy);
- MRI of brain study with intravenous gadolinium contrast (within 28 days prior to initiation of study therapy).
- Collection of slides/tumor blocks for molecular and immune profiling. (anytime prior to initiation of study therapy)
- Histologic confirmation (any time prior to initiation of study therapy):
 - Diagnostic confirmation of diffuse glioma by Laboratory of Pathology at NIH
 - Confirmation of *IDH1/2* mutation by DNA sequencing. If patient does not have this test, it can be done at the Laboratory of Pathology at NIH.
 - Tumor specific mutation burden analysis performed at NIH.

2.3 PARTICIPANT REGISTRATION AND STATUS UPDATE PROCEDURES

Registration and status updates (e.g., when a participant is taken off protocol therapy and when a participant is taken off-study) will take place per CCR SOP ADCR-2, CCR Participant Registration & Status Updates found at: <https://ccrod.cancer.gov/confluence/pages/viewpage.action?pageId=73203825>

2.3.1 Screen Failures

Screen failures are defined as participants who consent to participate in the clinical trial but are not subsequently assigned to the study intervention or entered in the study. A minimal set of screen failure information is required to ensure transparent reporting of screen failure participants, to meet the Consolidated Standards of Reporting Trials (CONSORT) publishing requirements and to respond to queries from regulatory authorities. Minimal information includes demography, screen failure details, eligibility criteria, and any serious adverse event (SAE).

Individuals who do not meet the criteria for participation in this trial (screen failure) because of a reversible medical conditions, such as kidney dysfunction may be rescreened.

2.3.2 Treatment Assignment Procedures (For registration purposes only):

Cohort

Number	Name	Description
1	HMP	IDH-mutant gliomas patients with hypermutated phenotype (HMP)

2	NHMP	IDH-mutant gliomas patients with non-hypermutated phenotype (NHMP)
---	------	--

Arm

Number	Name	Description
1	Nivolumab	IV Nivolumab

Arm assignment

Subjects in Cohort 1 and 2 will be directly assigned to Arm 1.

2.4 BASELINE EVALUATION

Within 14 days prior to first dose, unless otherwise specified:

- Concomitant Medications
- MRI of the brain study with intravenous gadolinium contrast (within 28 days).

Tests done at screening do not need to be repeated at baseline if performed in designated time frame prior to start of study drug.

- EKG
- Collection of MDASI (For English speaking subjects only)
- Collection of blood for research (See Section [5.1](#))

3 STUDY IMPLEMENTATION

3.1 STUDY DESIGN

This is a phase II study to evaluate the efficacy of treatment with nivolumab in glioma patients with or without HMP.

The study will be conducted in 2 stages.

During stage 1 of the study, 10 patients with HMP and 15 patients with NHMP will be accrued simultaneously into Cohorts 1 (HMP) and 2 (NHMP).

If 9 or more patients with HMP (Cohort 1) progress by 6 months, the Cohort 1 will be terminated early; otherwise, additional 19 patients will be accrued in stage II, resulting in a total sample size of 29.

If 3 or more patients with NHMP (Cohort 2) are progression-free at 6 months, the Cohort 2 will be moved to stage II and additional 15 patients will be accrued, resulting in a total sample size of 30.

All patients will be treated with nivolumab at a flat dose of 240 mg intravenously every 2 weeks (+/- 3 days) for cycles 1 through 2, then at a flat dose of 480 mg every 4 weeks for cycles 3-16. Treatment will be discontinued after 20 treatments given within 64 weeks.

One cycle is 4 weeks (+/- 3 days).

Study assessments presented in the Study Calendar (Section [3.5](#)).

3.2 DRUG ADMINISTRATION

Treatment will be routinely administered on an outpatient basis. Nivolumab will be administered through IV infusion over 30-60 minutes at a flat dose of 240 or 480 mg. See Section [14.1.5](#) for more details about study agent administration.

Vital signs will be measured within 1 hour before and after drug infusion.

If the eligible patients receive re-radiation immediately after pathology proving recurrent disease, additional proof of disease progression after re-radiation therapy is needed prior to the study treatment.

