4.2 PROHIBITED THERAPIES

- Other investigational drugs.
- Any cancer therapy other than nivolumab while patient is on the study.
- Stereotactic boost radiotherapy or other forms of local treatment such as the Gliadel wafer.

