6.3.4 Progression-free survival

Progression free survival is defined from the day of study entry until imaging is confirmed to show disease progression. Given the anticipated high rate of pseudo progression, patients with worsening lesions but without significant clinical decline may continue on treatment at the PI discretion. Subsequent confirmation of disease progression will mandate that the date of progression be defined as the date imaging worsening was first discovered. Patients who undergo diagnostic biopsy or resection uncovering evidence of pseudo progression will NOT be declared as having disease progression and will be able to resume protocol treatment.

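### Progression before nivolumab is required only after one kind of re-radiation, so patients stable or responding after other post-recurrence therapy are eligible as written and may raise PFS6

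*Combined protocol and SAP*

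**What the plan says.** Inclusion criterion 2.1.1.1 reads: "Patients must have recurrent diffuse glioma (histologically confirmed by NIH Laboratory of Pathology", with an IDH mutation. The exclusions in 2.1.2 that touch other treatment of the tumour are "Patients who are receiving any other investigational agents" and "Patients who have a history of receiving immune therapy". Section 4.2 prohibits "Any cancer therapy other than nivolumab while patient is on the study", so other treatment must have stopped by entry. Screening (2.2.2) requires "MRI of brain study with intravenous gadolinium contrast (within 28 days prior to initiation of study therapy" but names no finding that the scan must show. None of 2.1.1, 2.1.2, 2.2.2 or 2.4 asks for progression since the last therapy, a washout, or a limit on the time since recurrence.

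The one demand for progression stands in section 3.2, Drug Administration: "If the eligible patients receive re-radiation immediately after pathology proving recurrent disease, additional proof of disease progression after re-radiation therapy is needed" before nivolumab starts. It applies only to re-radiation given immediately after pathology-proven recurrence.

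The PFS clock starts at entry (6.3.4): "Progression free survival is defined from the day of study entry until imaging is confirmed to show disease progression". Section 10.1.1 tests PFS6 in each cohort against a fixed rate: 0.10 for HMP and 0.186 for NHMP.

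**The concern.** Section 3.2 treats pathology-proven recurrence as insufficient once re-radiation has followed it. The same reasoning applies to systemic treatment given after recurrence, but no rule covers that case. A patient can recur, receive chemotherapy, stabilise or respond, stop, and enter the trial with no evidence that the tumour is growing.

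The trial has no concurrent control. A patient whose disease was controlled shortly before entry is more likely to be progression-free six months later whatever nivolumab does. If enough such patients enter, the count can reach the success threshold without drug activity. Measurable disease is no safeguard, because 10.2.2 requires it only for evaluating objective response.

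**Working it through.** **Inputs from the plan (10.1.1).**
- HMP: 10 patients in stage I, continue with 2 or more progression-free; 19 more; claim with 6 or more of 29; null 0.10, alternative 0.30.
- NHMP: 15 patients in stage I, continue with 3 or more; 15 more; claim with 10 or more of 30; null 0.186, alternative 0.386.
- Section 1.2.7: 6 of the first 15 NHMP patients were progression-free at 6 months.

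**Assumed inputs.** The documents give neither the number *k* of entrants with controlled disease nor their PFS6, *s*. I take *k* = 1, 3, 6 and *s* = 0.3 to 0.6, with nivolumab inert.

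**Formula.** With stage sizes n1 and n2, continuation threshold g and final threshold r:

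P(claim) = Σ over x from g to n1 of P[Bin(n1, p) = x] × P[Bin(n2, p) ≥ r − x].

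For a mixed cohort of N patients, p = p0 × (1 − k/N) + s × k/N.

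**Step 1: the plan's own figures.** HMP gives a type I error of 0.047 and power of 0.805, matching the stated 0.05 and 0.8. NHMP gives 0.039 and 0.775, matching the 77.5% power in 1.2.7. The designs hold their error rate if every entrant has the null PFS6.

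**Step 2: mixed cohorts, seen from the start of the trial.** Worked example, HMP with k = 3: p runs from 0.10 × 26/29 + 0.3 × 3/29 = 0.121 to 0.10 × 26/29 + 0.6 × 3/29 = 0.152, and P(claim) runs from 0.097 to 0.208.

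| Controlled-disease entrants | HMP, of 29 | NHMP, of 30 |
|---|---|---|
| 0 | 0.047 | 0.039 |
| 1 | 0.06–0.09 | 0.04–0.06 |
| 3 | 0.10–0.21 | 0.06–0.12 |
| 6 | 0.17–0.45 | 0.08–0.27 |

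**Step 3: NHMP as it stands.** With 6 of 15 already counted, a claim needs 10 − 6 = 4 or more of the next 15.
- No such patient: P[Bin(15, 0.186) ≥ 4] = 0.30.
- One such patient among the 15: p runs from 0.186 × 14/15 + 0.3/15 = 0.194 to 0.186 × 14/15 + 0.6/15 = 0.214, and the probability is 0.33–0.40.

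The 0.30 is conditional on the observed stage I result and is not a type I error of the design. The part that an eligibility change could affect is the step from 0.30 to 0.33–0.40.

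**The case against.** Four objections carry weight.

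*Recurrent may be read as needing treatment now.* Section 10.1.1 draws its benchmarks from recurrent disease, and investigators may in practice enrol only patients who are progressing. That is plausible, and nothing in the documents shows that a controlled patient was enrolled. But the criterion does not say so, and the 3.2 rule would be largely redundant if it did. The gap in the text stands; how often it is used is unknown.

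*The direction of bias depends on sources not shown.* If the benchmark series also admitted patients with controlled disease, the nulls already include some of this effect. The documents do not give those series' entry criteria. A reader might infer a certain upward bias in both cohorts; only a probable one is supported.

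*The gap is narrower than it may look.* A reader might infer that patients still receiving other therapy can be treated on study. Sections 4 and 4.2 rule that out. A reader might also infer that re-radiation after recurrence seen only on imaging is clearly uncovered. That depends on 2.1.1.1: if the recurrence itself must be confirmed histologically, such a patient may not qualify; if histology of the glioma is enough, as the screening list in 2.2.2 suggests, the patient does.

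*The numbers are assumed.* This is correct. With one such patient the effect is small, and for NHMP the start-of-trial figures no longer describe the decision that remains.

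**Conclusion.** As written, 2.1.1.1 and 3.2 together require progression at entry only after re-radiation given immediately after pathology-proven recurrence. Patients stable or responding after stopping other post-recurrence therapy are eligible, and they would probably raise PFS6 against the fixed nulls, provided the benchmark series enrolled patients progressing at entry.

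The size is a sensitivity range, not an estimate. Three such patients would take either cohort's start-of-trial error above the stated 0.05 across the whole assumed PFS6 range; one would do so throughout for HMP but only in the upper part of the range for NHMP. A reader might infer that the 6 successes in NHMP stage I are inflated. The documents do not support that: 1.2.7 gives their WHO grades but nothing on disease control at entry.

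This is worth correcting because the rule the plan does state is too narrow and the correction is cheap.

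**What to change.** Reconcile 2.1.1.1 and 3.2 by stating the requirement once, in the eligibility list: any non-surgical tumour-directed therapy given after the qualifying recurrence must be followed by documented progression before study entry. The same edit should make clear whether the recurrence itself needs histological confirmation, which settles the imaging-only case. Exempting surgery leaves one route open, since a recently resected patient without residual tumour also enters without current progression; the report should describe any such patients.

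For patients already treated in either cohort, record from source whether progression after the last such therapy was documented. Report PFS6 with and without those lacking it, as a descriptive sensitivity analysis that leaves the decision rule unchanged. The subsets will be small, and in NHMP the amended criterion can govern only patients not yet enrolled.

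The cost is one eligibility line, checked against prior records and the MRI already required within 28 days, plus a records review. A few patients with controlled disease would have to wait until progression, which slightly slows accrual.

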3.3 DOSE MODIFICATIONS

There are no planned dose reductions for nivolumab.

The tables below outline the criteria for delaying (then restarting) or stopping treatment by toxicity type.

Treatment will be discontinued if AE is not resolved for 4 weeks.

Skin Rash and Oral Lesions	Management
Grade 1	Continue treatment. No change in dose *.
Grade 2	Hold* until \leq Grade resolved. Consider steroid treatment $>$ 5-7 days Resume at same dose level.
Grade 3	Hold* until \leq Grade 1. Resume at same level at investigator discretion
Grade 4	Off protocol therapy
*Patients with purpuric or bullous lesions must be evaluated for vasculitis, Steven-Johnson syndrome, TEN, and autoimmune bullous disease including oral lesions of bullous pemphigus/pemphigoid. Pruritus may occur with or without skin rash and should be treated symptomatically if there is no associated liver or GI toxicity. Note skin rash typically occurs early and may be followed by additional events particularly during steroids tapering.	
Recommended management: See AE management guidelines (Appendix C)	

Liver Function AST/ALT/T. Bili *	Management
Grade 1	Continue treatment
Grade 2	Hold until less than or equal to Grade 1. Resume at same dose level. Consider steroid treatment if persists $>$ 5-7 days or worsens.

Liver Function AST/ALT/T. Bili *	Management
Grade 3	Off protocol therapy
Grade 4	Off protocol therapy
Continued treatment of active immune mediated hepatitis may exacerbate ongoing inflammation. Holding drug to evaluate LFT changes and early treatment are recommended. LFT changes may occur during steroid tapers from other events and may occur together with other GI events including cholecystitis/pancreatitis.	
Recommended management: See Hepatic AE management algorithm (Appendix C)	
* Total bilirubin not used for determining AEs in patients with Gilbert syndrome.	

Renal Function Serum Creatinine	Management
Grade 1	Continue treatment.
Grade 2	Hold until \leq Grade 1. Resume at same dose level.
Grade 3	Hold until \leq Grade 1. Resume at same dose level.
Grade 4	Off protocol therapy
For Grade 2 or greater, consider renal biopsy. Corticosteroids may be required for Grade 2/3, high dose for grade 4.	
Recommended management: see Renal AE management algorithm (Appendix C)	

Diarrhea/ Colitis	Management
Grade 1	Diarrhea/asymptomatic colitis, continue treatment at PI discretion.
Grade 2	Hold until \leq Grade 1 or baseline. Consider steroid treatment if persists $> 5-7$ days.
Grade 3	Off protocol therapy.
Grade 4	Off protocol therapy.
Patients with grade 2 symptoms but normal colonoscopy and biopsies may be retreated after resolution.	
Patients with grade 2 persistent symptoms greater than 14 days who require steroids should be taken off study treatment.	
Please evaluate pituitary function prior to starting steroids if possible without compromising acute care.	
Evaluation for all patients for additional causes includes C. diff , acute and self-limited infectious and foodborne illness, ischemic bowel, diverticulitis, and IBD.	
Recommended management: see GI AE management Algorithm (Appendix C).	

Pancreatitis Amylase/Lipase	Management
Grade 1	Continue treatment if asymptomatic.
Grade 2	Hold until \leq Grade 1. Resume at same dose level if asymptomatic. Asymptomatic Grade 2 is defined as elevation of both amylase and lipase.

Pancreatitis Amylase/Lipase	Management
Grade 3	Off protocol therapy
Grade 4	Off protocol therapy

Patients may develop symptomatic and radiologic evidence of pancreatitis as well as DM and DKA. Lipase and/or amylase elevation may occur during the period of steroid withdrawal and with other immune mediated events or associated with colitis, hepatitis, and patients who have asymptomatic lipase and/or amylase elevation typically have self-limited course and may be retreated.
 
For treatment management of symptomatic pancreatitis please follow the Hepatic Adverse Event Management Algorithm (Appendix C).
	

Pneumonitis	Management
Grade 1	Hold dose pending evaluation and resolution to baseline including baseline pO ₂ . Resume; no change in dose after pulmonary and/or ID consultation
Grade 2	Hold dose pending evaluation and resolution to baseline including baseline pO ₂ . Resume; no change in dose after pulmonary and/or ID consultation if lymphocytic pneumonitis is excluded. Off study if grade 2 symptoms do not improve or worsen after 2 weeks of steroids and dose delay.
Grade 3	Off protocol therapy.
Grade 4	Off protocol therapy.

Distinguishing inflammatory pneumonitis is often a diagnosis of exclusion for patients who do not respond to antibiotics and have no causal organism identified including influenza. Most patients with respiratory failure or hypoxia will be treated with steroids. Bronchoscopy may be required and analysis of lavage fluid for lymphocytic predominance may be helpful. Patients with new lung nodules should be evaluated for sarcoid like granuloma. Please consider recommending seasonal influenza killed vaccine for all patients.
 
Recommended management: See Pulmonary Adverse Event Management Algorithm (Appendix C).
	

Other GI Nausea - Vomiting	Management
Grade 1	No change in dose.
Grade 2	Hold pending evaluation for gastritis duodenitis and other immune adverse events or other causes. Resume at same dose level after resolution to \leq Grade 1.
Grade 3	Hold pending evaluation until \leq Grade 1. Resume at same dose level. If symptoms do not resolve within 7 days with symptomatic treatment patients should go off protocol therapy
Grade 4	Off protocol therapy.

Other GI Nausea - Vomiting	Management
Patients with grade 2 or 3 N-V should be evaluated for upper GI inflammation and other immune related events.	

Fatigue	Management
Grade 1	No change in dose.
Grade 2	No change in dose
Grade 3	Hold until \leq Grade 2. Resume at same dose level
Fatigue is the most common adverse event associated with immune checkpoint therapy. Grade 2 or greater fatigue should be evaluated for associated or underlying organ involvement including pituitary, thyroid, and hepatic, or muscle (CPK) inflammation	

Neurologic events	Management
Grade 1	Hold dose pending evaluation and observation. Resume with no change in dose.
Grade 2	Hold dose pending evaluation and observation. Hold until \leq Grade 1.* Off protocol therapy if treatment with steroids is required. Resume at same dose level for peripheral isolated n. VII (Bell's palsy)
Grade 3	Off protocol therapy
Grade 4	Off protocol therapy
*Patients with any CNS events including aseptic meningitis, encephalitis, or myopathy, peripheral demyelinating neuropathy, cranial neuropathy (other than peripheral n. VII), GB syndrome, myasthenia gravis should be off protocol therapy.	
Recommended management: See Neurologic Adverse Event Management Algorithm (Appendix C)	

Endocrine Hypophysitis Adrenal Insufficiency	Management
Grade 1	Asymptomatic TSH elevation *. Treatment may continue while having endocrine evaluation. endocrine consult is recommended.
Grade 2	Hold until patients are on a stable replacement hormone regimen. If treated with steroids patients must be stable off steroids for two weeks. Resume at same dose level.
Grade 3	Off protocol therapy
Grade 4	Off protocol therapy
Note all patients with symptomatic pituitary enlargement, exclusive of hormone deficiency, but including severe headache or enlarged pituitary with enhancement on MRI should be considered grade 3 events. Isolated thyroid or testosterone deficiency may be treated as grade 2 if there are no other associated deficiencies and adrenal function is monitored.	

Endocrine Hypophysitis Adrenal Insufficiency	Management
	Please evaluate pituitary function before beginning steroid therapy or replacement therapy of any kind. *Note patients with thyroiditis may be retreated on replacement therapy. Patients must be evaluated to rule out pituitary disease prior to initiating thyroid replacement.
	Recommended management: See Endocrine Management Algorithm (Appendix C)

Fever	Management
Grade 1	No change in dose.
Grade 2	Hold until \leq Grade 1. Resume at same dose level.
Grade 3	Hold until \leq Grade 1. Resume at same dose level.
Grade 4	Off protocol therapy
Patients with fever should be evaluated as clinically appropriate. Patients may experience isolated fever during infusion reactions or up to several days after infusion. Evaluation over the course of 1-2 weeks should be done for other autoimmune events that may present as fever.	

ALL OTHER EVENTS: NOT AGENT RELATED OR AGENT RELATED NON-IMMUN RELATED	Management
Grade 1	No change in dose
Grade 2	Can continue treatment at PI discretion.
Grade 3	Hold until \leq Grade 1 continue at investigator discretion with the following exception: Grade 3 lymphopenia or asymptomatic amylase or lipase does not require dose delay
Grade 4	Off protocol therapy, with the following exceptions: 
Grade 4 neutropenia \leq 7 daysGrade 4 lymphopenia or leukopenia or asymptomatic amylase or lipaseIsolated Grade 4 electrolyte imbalances/abnormalities that are not associated with clinical sequelae and are corrected with supplementation/appropriate management within 72 hours of their onsetGrade 4 drug-related endocrinopathy adverse events, such as, hyper- or hypothyroidism, or glucose intolerance, which resolve or are adequately controlled with physiologic hormone replacement (corticosteroids, thyroid hormones) or glucose-controlling agents,

ALL OTHER EVENTS: NOT AGENT RELATED OR AGENT RELATED NON-IMMUN RELATED	Management
	respectively, may not require discontinuation after discussion with and approval from the BMS Medical Monitor.
Recommended management: As clinically indicated	

ALL OTHER EVENTS: IMMUNE RELATED	Management
Grade 1	No change in dose
Grade 2	Hold until \leq Grade 1 OR baseline. When resolved or following steroids, resume at same dose level. 
Exception: Nivolumab should be discontinued for any grade 2 drug-related uveitis, eye pain or blurred vision that does not respond to topical therapy and does not improve to Grade 1 severity within the re-treatment period OR requires systemic treatment
Grade 3	
Any grade 3 or 4 drug-related laboratory abnormality or electrolyte abnormality, not associated with underlying organ pathology, that does not require treatment except for electrolyte replacement OR hormone/steroid replacement does not require treatment discontinuation.Any grade 2 or 3 drug-related uveitis or eye pain or blurred vision that does not respond to topical therapy and does not improve to Grade 1 severity within the re-treatment period OR requires systemic treatment requires treatment discontinuation
Grade 4	Off protocol therapy, with the following exceptions: 
Grade 4 neutropenia \leq 7 daysGrade 4 lymphopenia or leukopenia or asymptomatic amylase or lipaseIsolated Grade 4 electrolyte imbalances/abnormalities that are not associated with clinical sequelae and are corrected with supplementation/appropriate management within 72 hours of their onsetGrade 4 drug-related endocrinopathy adverse events, such as, hyper- or hypothyroidism, or glucose intolerance, which resolve or are adequately controlled with physiologic hormone replacement (corticosteroids, thyroid hormones) or glucose-controlling agents,

ALL OTHER EVENTS: IMMUNE RELATED	Management
	respectively, may not require discontinuation after discussion with and approval from the BMS Medical Monitor.
Recommended management: As clinically indicated.	

